1. Test effectiveness of unlimited daily, message-based psychotherapy (MBP) for depression, compared to weekly traditionally delivered, videoconferencing-based psychotherapy (VBP). Level 1 conditions: unlimited MBP and weekly VBP.
2. Develop an evidence-based treatment sequence for those who do not respond to either MBP or VBP. Level 2 conditions for participants who do not respond to treatment: MBP+VBP_{weekly} (switch from MBP to weekly VBP with MBP), MBP+VBP_{monthly} (switch from MBP to monthly VBP with MBP), VBP_{weekly}+MBP (switch from VBP to weekly VBP with MBP), and VBP_{monthly}+MBP (switch from VBP to monthly VBP with MBP).

Hypothesis 1: Compared to those randomized to weekly video care at baseline, patients randomized to message-based care will have greater improvements in depression (1a) and social functioning (1b), be more likely to show a treatment response (1c), and be more likely to experience remission (1d) at 5 and 12 weeks of care. Hypothesis 2: For those who fail to respond to treatment from baseline to 5 weeks, those re-randomized to receive (or retain) weekly video care will have greater improvements in depression and be more likely to show a response to treatment than those randomized to monthly video care. Hypothesis 3 (moderator): Baseline anxiety will moderate improvement in depression such that those with greater anxiety will have better response to message-based care at 5 and 12 weeks than to video-based care. Exploratory Aims: Exploratory evaluation of differences among groups in treatment engagement by week 5, ratings of therapeutic alliance at weeks 4 and 10, ratings of

quality of care and amount helped by treatment at week 10, and ratings of goal satisfaction, plans to continue using treatment, and likelihood to recommend treatment to others at week 12.

Sample Size and Power: We propose to screen 4,789 potential participants, anticipating we will enroll 1,250 participants to arrive at a final sample of 1,000 evaluated participants, assuming a 20% dropout rate by the last assessment. In our previous psychotherapy studies, dropout rates have been on the order of 10% by final assessment. In our recent on-line studies with Google Verily, drop out has been on the order of 20%. Our large incentive arm, tested in Phase 1, is based on the incentive analyses done on the Baseline Mood Study at Verily.

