Level 1 Power: For the quantitative primary outcome (PHQ-9) we have greater than 80% power to detect a 0.20 standard deviation across groups which corresponds to a clinically meaningful small difference. For a binary success indicator, we will consider a 50% reduction in PHQ-9 from baseline to week 5, and we have greater than 80% power to detect an absolute difference of 10% (e.g., 60% of subjects with >50% improvement versus 70% of subjects with >50% improvement).

Level 2 Power: The primary comparison in the second stage is the comparison of the Ultimate Plan (UP; MBP with weekly VBP) versus the Premium Plan (PP; MBP with monthly VBP) for each of the first stage randomization groups (MBP and VBP). We expect a second stage analysis sample of 324 subjects, and this corresponds to 80% power to detect a 0.32 standard deviation difference across the UP and PP groups when pooling across the primary MBP and VBP strata. Our primary second stage analysis will construct an overall UP versus PP difference stratifying on first stage randomization, and secondary analysis will consider the UP versus PP difference within the MBP and VBP groups separately.

Accounting for Provider Effects: Each provider will treat both MBP and VBP patients. Therefore, our primary analyses will all cluster on provider either using linear mixed models or generalized estimating equations to yield valid statistical inference. However, since treatment condition will vary within provider, the impact of provider clustering is to effectively balance or control for provider effects. Therefore, our power calculations are conservative since they do not account for the potential increase in precision associated with control for provider effects. Such within-provider randomization is in contrast to traditional cluster randomized trials where providers treat all patients in one study condition and thus increase variability associated with treatment comparisons through the well-known intra-cluster correlation coefficient.

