Statistical Analyses: See Table 2 for analyses by hypothesis. Treatment disengagement, treatment response, and remission will be analyzed using chi-square tests and Cramér V effect sizes. 2-level linear mixed effects models using full information maximum likelihood (FIML) and an unstructured covariance matrix with client nested within clinician will be used for analyses at a single timepoint. Models predicting binary outcomes at a single timepoint will be evaluated using 2-level logistic regression models with Cholesky factorization with client nested within clinician, with Level 2 condition as the independent variable. Effect sizes for these models will be computed via pooled standard deviations of conditions at that timepoint.

Models assessing changes across time will be evaluated using 3-level mixed effects regression models with timepoint nested within client nested within clinician using FIML and an unstructured covariance matrix. Client-level effects will be allowed to randomly vary, and clinician will be a clustering variable with condition approximately balanced within clinicians. Analyses with time from baseline to week 12 will include a spline variable to account for differences in outcome trajectories from baseline to week 5 and from week 6 to week 12.

The mixed-effects models will utilize all available data. Prior research has demonstrated equivalence of longitudinal mixed model analyses using imputed versus non-imputed data (e.g., between multiple imputation and FIML).¹³ Theoretically, there is no reason to expect substantial differences between FIML and MI with a reasonable sample size and complete predictors.¹⁴ Thus, missing data will not be imputed. Cohen's *d* clinical outcome effect sizes for the model predicting PHQ-9 scores by Level 2 condition from weeks 6 to 12 will be computed as the difference between model-estimated means divided by the pooled standard deviations when the second condition

was assigned at week 6. All remaining clinical outcome effect sizes will be computed as the difference between model-estimated means divided by the pooled baseline standard deviations.

We will use the Benjamini-Hochberg procedure to account for Type 1 error by adjusting for familywise error within hypothesis families (e.g., within Hypotheses 1a to 1d; within Hypothesis 2). *P* values and effect sizes with 95% confidence intervals will be reported, as appropriate.¹⁵

Table 2. Analyses by Hypothesis

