Hypothesis	Timepoint(s)	Statistical Test	Contrast/analysis of interest
1a: Compared to those randomized to weekly video care at baseline, patients randomized to message-based care will have greater improvements in depression	Baseline to W5	3-level mixed effects model	MBP vs VBP
1b: Compared to those randomized to weekly video care at baseline, patients randomized to message-based care will have greater improvements in social functioning	Baseline to W12	3-level mixed effects model	MBP vs VBP
1c: Compared to those randomized to weekly video care at baseline, patients randomized to message-based care will be more likely to show a treatment response at 5 and 12 weeks of care.	Between W3 to W5 / W12	Chi-square tests	MBP vs VBP
1d: Compared to those randomized to weekly video care at baseline, patients randomized to message-based care will be more likely to experience remission at 5 and 12 weeks of care.	Between W3 to W5 / W12	Chi-square tests	MBP vs VBP
2: For those who fail to respond to treatment from baseline to 5 weeks, those re-randomized to receive (or retain) weekly video care will have greater improvements in depression than those randomized to monthly video care	W6 to W12	3-level mixed effects model with time centered at week 6	MBP+VBP _{weekly} vs MBP+VBP _{monthly} ; VBP _{weekly} +MBP vs VBP _{monthly} +MBP
2: For those who fail to respond to treatment from baseline to 5 weeks, those re-randomized to receive (or retain) weekly video care will be more likely to show a response to treatment than those randomized to monthly video care	W12	Chi-square test	MBP+VBP _{weekly} vs MBP+VBP _{monthly} ; VBP _{weekly} +MBP vs VBP _{monthly} +MBP
3 (moderator): Baseline anxiety will moderate improvement in depression such that those with greater anxiety will have better response to message-based care at 5 and 12 weeks than to video-based care.	Baseline to W12	3-level mixed effects model, with mean-centered baseline GAD-7	MBP vs VBP

Exploratory: We will explore whether there will be differences among groups in treatment engagement by week 5	Between W3 to W5	Chi-square test	MBP vs VBP
Exploratory: We will explore whether there will be differences among groups in ratings of therapeutic alliance	W4 / W10	2-level mixed effects models	W4: Level 1 conditions (MBP vs VBP); W10: Level 2 conditions (MBP vs VBP; MBP+VBP _{monthly} vs MBP+VBP _{weekly} ; VBP _{monthly} +MBP vs VBP _{monthly} +MBP)

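### Hypothesis 1a claims greater improvement in depression at 5 and 12 weeks, but Table 2 names no unmoderated Level 1 test of mean PHQ-9 after week 5

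*Combined protocol and SAP*

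**What the plan says.** Under Hypothesis 1 in Section 8.0, the message-based arm "will have greater improvements in depression (1a) and social functioning (1b") and, at the end of the same sentence, will "be more likely to experience remission (1d) at 5 and 12 weeks of care". Read naturally, the two timepoints govern all four parts.

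The Statistical Analyses paragraph sends the reader to Table 2 for the analysis of each hypothesis. The rows that bear on this point are:

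| Row | Outcome | Timepoint | Test |
|---|---|---|---|
| 1a | Depression | "Baseline to W5" | 3-level mixed model, MBP vs VBP |
| 1b | Social functioning | Baseline to W12 | 3-level mixed model, MBP vs VBP |
| 1c, 1d | Response, remission | W3 to W5, and W12 | Chi-square, MBP vs VBP |
| 2 | Depression, response | W6 to W12, and W12 | Weekly vs monthly video, re-randomised non-responders only |
| 3 | Depression, moderated by baseline GAD-7 | Baseline to W12 | 3-level mixed model, MBP vs VBP |

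Level 1 Power identifies the outcome concerned: "For the quantitative primary outcome (PHQ-9) we have greater than 80% power to detect a 0.20 standard deviation across groups". It gives no timepoint for that comparison. The sample size is set "to arrive at a final sample of 1,000 evaluated participants, assuming a 20% dropout rate by the last assessment".

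On missing data, "The mixed-effects models will utilize all available data" and "Thus, missing data will not be imputed". The binary outcomes are handled differently: "Treatment disengagement, treatment response, and remission will be analyzed using chi-square tests". Benjamini-Hochberg adjustment is applied within families, with 1a to 1d given as one family.

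**The concern.** If Table 2 is followed as written, the 12-week part of Hypothesis 1a has no test on the quantitative primary outcome, although PHQ-9 is collected weekly to week 12 and enrolment allows for dropout up to the last assessment.

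This leaves room for a decision after the data are seen. A favourable week-12 mean difference, from row 3's model or a new one, could be reported as support for 1a although it sits outside the Hypothesis 1 adjustment. An unfavourable one could be called unplanned. If 1c and 1d are not significant at week 12, the hypothesis text and the table give a reader different answers on whether the 12-week claim in 1a failed or was never tested.

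A second, minor matter lies in the exploratory rows. The alliance row at W10, and the W12 row on goal satisfaction, continuation and recommendation, list MBP versus VBP among Level 2 conditions. Under Section 3.0 and the Randomization text of Section 5.1, people still on one modality alone at that stage are Level 1 responders (the plan does not say where someone with neither a PHQ-9 nor a CGI-I is placed). That contrast is selected on a post-randomisation outcome, and the plan does not say so.

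**Working it through.** **Plan's own figures.** Two-sided 0.05 and 1:1 allocation are assumed, since Section 8.0 states neither; 1,000 evaluated gives 500 per arm.

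- Mean PHQ-9 at 0.20 SD: 0.20 × √(500/2) = 3.162; power = Φ(3.162 − 1.960) = 0.885. This agrees with the stated figure of more than 80%.
- Response at 60% vs 70%: power 0.913, again more than 80%.
- Dropout: 1,000 / (1 − 0.20) = 1,250 enrolled, so 250 are expected to be lost by the last assessment.

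No stated number is wrong. The defect is the mismatch between the hypothesis and the table.

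**What is left out.** Table 1 in Section 4.5 lists 12 post-baseline weekly assessments, and Section 5.2 puts a PHQ-9 in each. Row 1a uses W1 to W5. The other 7 of 12 (58%) enter no unmoderated Level 1 test of the mean.

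**Cost of relying on cut-points at week 12.** Assume a normal outcome with a 0.20 SD shift present at W12. A VBP rate p1 then implies an MBP rate p2 = Φ(Φ⁻¹(p1) + 0.20). With 500 per arm, power = Φ[(|p2 − p1| − 1.960·SE₀)/SE₁], where SE₀ is pooled and SE₁ unpooled.

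| p1 | p2 | Power |
|---|---|---|
| 0.20 | 0.261 | 0.624 |
| 0.30 | 0.373 | 0.684 |
| 0.40 | 0.479 | 0.709 |
| 0.50 | 0.579 | 0.711 |
| 0.60 | 0.675 | 0.693 |
| 0.70 | 0.766 | 0.650 |

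For example, at p1 = 0.60: (0.0749 − 1.960 × 0.0304)/0.0303 ≈ 0.50, and Φ(0.50) ≈ 0.69. The 60% is the plan's own example rate; the rest of the range is assumed. The mean comparison has 0.885 throughout.

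The difference detectable with 80% power is (1.960 + 0.842) × √(2/500) = 0.177 SD for the mean, against 0.223 SD (p1 = 0.50) to 0.245 SD (p1 = 0.20) for a cut-point.

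**Cost of adding the test.** By our count the family holds 6 tests: 1a, 1b, two for 1c and two for 1d. Adding one makes 7.

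| Tests | Strictest step | Detectable difference at that step | Power at 0.20 SD |
|---|---|---|---|
| 6 | 0.05/6 = 0.0083 | 0.220 SD | 70.0% |
| 7 | 0.05/7 = 0.0071 | 0.223 SD | 68.2% |

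If 1b yields two tests, the count goes from 7 to 8, the step from 0.0071 to 0.0063 and the detectable difference from 0.223 to 0.226 SD. The strictest step decides the result only when no other test in the family passes.

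**Exploratory rows (illustration).** Let Z be a standard normal tendency to respond. The mean of Z is 0.644 in the top 60% and 0.497 in the top 70%. With 60% vs 70% response, the retained responders therefore differ by 0.497 − 0.644 = −0.147 before any modality effect. If Z correlates r = 0.3 to 0.7 with the rated outcome, the contrast moves by 0.147 × 0.3 = 0.044 to 0.147 × 0.7 = 0.103 SD, against the arm with the higher response rate. The documents do not give r.

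**The case against.** The strongest reply is that the plan means week 5 and the hypothesis sentence is merely loose. Table 2 is the operative list, and it repeats the two timepoints in rows 1c, 1d and 3 but not in 1a. The only timepoint in Level 1 Power is week 5, for the binary indicator. After that, non-responders in both arms move to combined care, so week 5 is the cleaner comparison of modalities. All of this is fair, and a week-5-only test is defensible. But row 1b also omits the phrase and still runs to W12, so the omission does not explain why 1a stops early. If week 5 is meant, the hypothesis should say so.

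A second reply is that row 3 already models PHQ-9 to W12 and, with mean-centred GAD-7, can give the arm contrast at average anxiety. That is true. The plan does not designate it as the test of 1a, and Hypothesis 3 lies outside the 1a to 1d family.

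A third reply is that the power comparison rests on assumptions. It does: the 0.20 SD may shrink once both arms receive combined care, and response is a within-person reduction rather than a cut on a single normal variable. At the plan's own 60% vs 70%, chi-square power is 91.3%. That is a larger shift, Φ⁻¹(0.70) − Φ⁻¹(0.60) = 0.271 SD, at which the mean test has Φ(0.271 × √250 − 1.960) ≈ 0.99, so the ordering is unchanged. The 20% dropout is a separate matter and plays no part in the gap, since both tests are computed at 500 per arm.

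The exploratory-row point is a different issue, and no hypothesis rests on it.

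**Conclusion.** The concern holds. The hypothesis text and Table 2 disagree on whether 1a extends to week 12, and under Table 2 the 12-week part of 1a is untested on the quantitative primary outcome within its own multiplicity family. Depression at week 12 is not ignored, but what remains is cut-point tests and a moderator model. On the stated assumptions (0.20 SD still present at W12, normality, 500 per arm, unadjusted two-sided 0.05), relying on the cut-points gives 62% to 71% power instead of 88.5%. This should be corrected, but it invalidates nothing else in the plan. The exploratory responder-only contrasts are a minor labelling fault, with an illustrative size of 0.04 to 0.10 SD.

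**What to change.** Reconcile the Hypothesis 1 sentence with Table 2 row 1a in one of two ways:

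- Keep the week-5 test and add a W12 MBP versus VBP contrast in model-estimated PHQ-9 by Level 1 assignment. Take it from the baseline-to-W12 spline model type already described in Section 8.0, and count it in the Hypothesis 1 Benjamini-Hochberg family.
- Or limit Hypothesis 1a to week 5 in the text.

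In either case, state that W12 comparisons by Level 1 arm compare starting strategies, because by then non-responders in both arms have moved to combined care.

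For the exploratory W10 and W12 rows, make the MBP versus VBP contrast by Level 1 assignment in all participants, and keep the Level 2 contrasts for the re-randomised pairs. If the responder-only contrast is kept, label it descriptive and non-randomised.

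The cost is SAP wording only: no new data and no new model type. The first option adds one test to the family, with the small loss at the strictest step shown above. The second costs one clause.
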